2.2.2.2. Per Protocol Set (PP)

All subjects in the ITT-i set without major protocol deviations that may have an impact on the efficacy analysis.

Decisions regarding which subjects are included in the per protocol set will be made before database lock on the following criteria. Subjects will be included in the PP set in case:

- Subjects missed at most 3 doses in total or at most 2 consecutive doses. On the day of randomization or the next day at least one dose needs to be taken.
- The actual treatment must be the same as the planned treatment
- No unblinding may have taken place
- Subjects may not violate inclusion criteria 2, 3, 5, and 12 and exclusion criteria 1, 6, 9, 12, and 13. For details of these in/exclusion criteria refer to [Table 5](#).
- Screening PRO assessments (Pre-existing Symptom Questionnaire and Flu-iiQ™ Module 1) performed on the ePRO device before randomization.
- Completed the pre-existing symptoms questionnaire and have at least 3 post-baseline Flu-iiQ™ measurements.
- Influenza antiviral as part of the SOC was started no later than Day 2 morning.
- Subjects did not switch to another influenza antiviral as a part of the SOC during the treatment period.

Table 5: Details of inclusion and exclusion criteria to be fulfilled for inclusion in the per protocol analysis set

Inclusion/Exclusion	Criterion number	Description
Inclusion	2	Present to the clinic with symptoms suggestive of a diagnosis of acute influenza and have at least 1 respiratory symptom and at least 1 systemic symptom, both scored as at least 'moderate' if the symptom did not pre-exist before influenza onset, or scored worse than usual if the symptom pre-existed as determined by subject's ratings on Module 1 of the Flu-iiQ™ and the Pre-existing Symptom Questionnaire in the ePRO device. Symptoms must include the following by category: 
 1. Respiratory symptoms: cough, sore throat, nasal congestion, 2. Systemic symptoms: headache, body aches or pain, feverishness, fatigue.
Inclusion	3	Tested positive for influenza A infection after the onset of symptoms, using a rapid influenza diagnostic test (RIDT) or, if available, a PCR-based or other rapid molecular diagnostic assay.
Inclusion	5	Enrollment and initiation of study drug treatment ≤ 72 hours after onset of influenza symptoms.
Inclusion	12	Subjects 13 to 65 years of age, inclusive must also have at least one of the following: 
 a. Cardiovascular or cerebrovascular disease (including congenital heart disease, chronic heart failure, coronary artery disease, or stroke: excluding isolated hypertension) b. Chronic lung disease (eg, asthma, chronic obstructive lung disease [COPD] or cystic fibrosis)

Inclusion/ Exclusion	Criterion number	Description
		c. Weakened immune system due to disease or medication (eg, subjects with human immunodeficiency virus [HIV], cancer, or chronic liver or kidney disease [presence of kidney damage for > 3 months, defined by structural or functional abnormalities of the kidney, with or without decreased GFR manifested by: pathological abnormalities; OR markers of kidney damage, including abnormalities in the composition of the blood or urine or abnormalities in imaging tests], or subjects taking chronic systemic steroids).
Exclusion	1	Received more than 1 dose of influenza antiviral medication (eg, OST or zanamivir), or any dose of ribavirin within 2 weeks, prior to first study drug intake, or received IV peramivir more than 1 day prior to screening.
Exclusion	6	Severely immunocompromised in the opinion of the investigator (eg, known cluster of differentiation 4 ⁺ [CD4 ⁺] count <200 cells/mm ³ , absolute neutrophil count <750/mm ³ , first course of chemotherapy completed within 2 weeks prior to screening, history of stem cell transplant within 1 year prior to screening, history of a lung transplant).
Exclusion	9	Taken any disallowed therapies before the planned first dose of study drug.
Exclusion	12	Subject has any condition that could prevent, limit, or confound the protocol-specified assessments (eg, subject is unable to swallow tablets, unable to complete PROs, or is illiterate), or in the opinion of the investigator, participation would not be in the best interest of the subject (eg, compromise the well-being).
Exclusion	13	Subject has presence of any pre-existing illness, clinically significant laboratory abnormalities, ECG findings, or physical examination findings that, in the opinion of the investigator, would place the subject at an unreasonably increased risk through participation in this study. The investigator should consider the laboratory parameter criteria for study drug discontinuation when screening a subject for enrollment.

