## **6. DOSAGE AND ADMINISTRATION**

During the treatment period, all subjects will receive study drug in a 1:1 ratio in 1 of the 2 treatment arms. Depending on the time of screening/enrollment, subjects will receive 1 dose

(evening) or 2 doses (morning and evening) of study drug on Day 1. Subjects may delay or bring forward administration of the second dose (by no more than 4 hours) only if the nominal timing for this second dose falls in the middle of the night. For subjects who receive only 1 dose of pimodivir or placebo on Day 1 (evening), dosing should continue until the morning of Day 6 so that all subjects receive 10 doses in total.

	Treatment Arm 1	Treatment Arm 2
Test Article(s)	Pimodivir (Day 1 through Day 5) + SOC treatment a,b	Placebo (Day 1 through Day 5) + SOC treatment a,b
Description	300 mg tablet	Placebo tablet
Dose per Delivery	Day 1 to Day 5 600 mg pimodivir (2 tablets)	Day 1 to Day 5 Placebo (2 tablets)
Frequency	Bid	Bid
Total Dose	1,200 mg	NAP
Delivery Methodc	Oral	Oral
Food/Fasting Requirement	No food requirements	No food requirements

Abbreviations: bid: twice daily; NAP: not applicable; SOC: standard-of-care.

a SOC treatment will be determined by the investigator based on local practice, and may include influenza antivirals and/or supportive care only. The choice to use influenza antivirals as part of the SOC should be made before randomization. The influenza antiviral should be started no later than Day 2 morning (up to noon). An influenza antiviral as part of the SOC cannot be changed (eg, switching one influenza antiviral for another) during the treatment period, with the exception that an influenza antiviral may be discontinued in the case of a suspected adverse event.

b Depending on the time of screening/enrollment, subjects will receive 1 dose (evening) or 2 doses (morning and evening) of study drug on Day 1. For subjects who receive only 1 dose of pimodivir or placebo on Day 1 (evening), dosing should continue until the morning of Day 6 so that all subjects receive 10 doses in total.

c Refer to the pharmacy manual/study site investigational product manual for additional guidance on study drug preparation, handling, and storage.

Study-site personnel will instruct subjects on how to store study drug for at-home use as indicated for this protocol.

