#### 9.1.2. Screening Phase

At the screening visit, after signing of the ICF/assent form (see Section [16.2.3](#) for more details), the overall eligibility of the subject to participate in the study will be assessed and documented in the eCRF. First study drug intake should take place immediately after all screening/baseline procedures have taken place and eligibility has been established. Screening/baseline assessments start at signing of the ICF/assent form. Note: It is recommended that the screening/baseline assessments are completed as quickly as possible, in order to start study drug treatment as soon as possible. However, if needed, screening/baseline assessments and establishment of eligibility can continue the next calendar day, in which case the first study drug intake will be on that day, immediately after establishing eligibility. For analysis purposes, the day of first study drug intake will be considered Day 1. Subjects who successfully meet all inclusion criteria and none of the exclusion criteria will be eligible for participation in the study.

The subject's characteristics, demographic data, medical and surgical history, and prestudy and concomitant medication, including influenza vaccination status, will be recorded. A virology test capable of distinguishing between influenza types A and B, will be carried out locally as part of

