2.2.2. Efficacy Analysis Sets

Efficacy will be analyzed on the intent-to-treat infected (ITT-i) set and by randomized treatment. The primary efficacy endpoint will also be analyzed on the Per Protocol set. The primary efficacy endpoint and the two most important secondary endpoints (ie, 'Incidence of treatment-emergent adjudicated influenza complications' and 'Incidence of hospital admission 28 days after treatment initiation') will also be analyzed on the intent-to-treat non-infected (ITT-ni) set and by randomized treatment.

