4.3. Treatment Compliance

Treatment compliance for pimodivir/placebo is calculated as the actual number of doses taken, as a percentage of the planned number of doses. The actual number of doses taken will be derived from the drug accountability information (DA domain) as the difference between the amount of drug dispensed and the drug returned (in case both amounts are known), otherwise treatment compliance will be missing.

For placebo or pimodivir this number needs to be divided by 2 as the study uses 300 mg tablets. The planned number of medication is 20 tablets of placebo or pimodivir hence the planned number of doses per medication equals 10 doses. Note that the planned number of doses is irrespective of whether the subject discontinued during the treatment phase.

Dosing compliance will be summarized descriptively in the treatment phase and by discontinuing the trial during the treatment period (Yes, No).

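### The per-protocol dosing rule joins its two missed-dose limits with 'or', so it admits subjects who missed 5, 6 or even 7 of 10 doses

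*SAP*

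**What the plan says.** SAP 2.2.2 adds a supportive analysis to the one on the ITT-i set: "The primary efficacy endpoint will also be analyzed on the Per Protocol set". SAP 2.2.2.2 opens with the general definition, "All subjects in the ITT-i set without major protocol deviations that may have an impact on the efficacy analysis", and then says that membership is decided before database lock on a list of criteria. The first criterion concerns dosing: "Subjects missed at most 3 doses in total or at most 2 consecutive doses". It continues: "On the day of randomization or the next day at least one dose needs to be taken".

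The remaining criteria cover actual versus planned treatment, unblinding, selected eligibility criteria, questionnaire completion, and the timing and switching of the background antiviral. None sets a minimum number of doses. Protocol 11.1 gives only a general definition based on major deviations and premature unblinding.

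The number of planned doses is fixed in SAP 4.3: "The planned number of medication is 20 tablets of placebo or pimodivir hence the planned number of doses per medication equals 10 doses". This holds for subjects who stop early too: "Note that the planned number of doses is irrespective of whether the subject discontinued during the treatment phase".

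**The concern.** In an inclusion criterion, 'or' means that either condition suffices. Elsewhere in the same list, the questionnaire criterion uses 'and' where two conditions must both hold, so a programmer following the text would code the dosing criterion as an alternative.

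Two consequences follow. The cap of 3 on the total never excludes a subject who avoids three misses in a row. The cap of 2 on consecutive misses never excludes a subject whose total is 3.

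The per-protocol analysis is there to show the treatment effect in subjects who broadly followed the regimen. A set that includes subjects who took half of it or less answers that question less well, and any dilution makes agreement or disagreement with the ITT-i result harder to interpret. Two statisticians could also build different sets from the same sentence.

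**Working it through.** **Inputs**

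- Planned doses (SAP 4.3): 20 tablets / 2 tablets per dose = 10. This agrees with 5 days × 2 doses = 10.
- Evening starters also have 10 slots (Protocol 6): "dosing should continue until the morning of Day 6 so that all subjects receive 10 doses in total".
- Rule as written (SAP 2.2.2.2): total missed ≤ 3 **or** longest run of misses ≤ 2.
- Early-dose condition (SAP 2.2.2.2): at least one dose among the first 4 slots for a morning start, or the first 3 for an evening start.
- Day 1 (Protocol 9.1.2): "For analysis purposes, the day of first study drug intake will be considered Day 1".

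**Maximum missed, by hand**

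Take k doses with no run of misses longer than 2.

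- *Counted from the first scheduled slot.* There are k + 1 gaps of at most 2 misses, so k + 2(k + 1) ≥ 10. With k = 2 the pattern fills at most 8 slots. Hence k ≥ 3 and at most 7 doses are missed.
- *Counted from first intake.* Slot 1 is always taken, leaving k gaps, so k + 2k ≥ 10. Hence k ≥ 4 and at most 6 doses are missed.

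**Simple examples** (T = taken, M = missed)

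| Pattern | Missed | Longest run | 'or' | 'and' |
|---|---|---|---|---|
| TMTMTMTMTM (one dose a day) | 5 | 1 | admitted | excluded |
| TTTTTTTMMM (stops after dose 7) | 3 | 3 | admitted | excluded |
| TMMTMMTMMT | 6 | 2 | admitted | excluded |
| TTTTTTMMMM (stops after dose 6) | 4 | 4 | excluded | excluded |

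**Full enumeration**

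There are 2^10 = 1,024 taken/missed sequences. For a morning start, the early-dose condition removes the 2^6 = 64 sequences with the first four slots all missed, leaving 960. Patterns admitted, by number missed:

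| Missed | 0 | 1 | 2 | 3 | 4 | 5 | 6 | 7 | Total |
|---|---|---|---|---|---|---|---|---|---|
| 'or' | 1 | 10 | 45 | 120 | 161 | 126 | 45 | 4 | 512 |
| 'and' | 1 | 10 | 45 | 112 | 0 | 0 | 0 | 0 | 168 |

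The difference is 512 − 168 = 344. Of these, 161 + 126 + 45 + 4 = 336 have 4 to 7 misses, and 120 − 112 = 8 have exactly three misses, all consecutive. No pattern with 8 or more misses passes.

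For an evening start, 'or' admits 511 (one fewer three-miss pattern), 'and' admits 168, and the maximum is again 7.

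Only 4 of the 120 seven-miss patterns pass: MTMMTMMTMM, MMTMTMMTMM, MMTMMTMTMM and MMTMMTMMTM. In all four the first scheduled slot is missed.

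Counted from first intake, there are 2^9 = 512 sequences. 'Or' admits 1 + 9 + 36 + 84 + 90 + 51 + 10 = 281, with a maximum of 6 missed. 'And' admits 1 + 9 + 36 + (84 − 7) = 123, with a maximum of 3.

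**The case against.** The strongest reply is that the set is supportive, the problem patterns are probably uncommon, and the sponsor very likely meant both limits to apply. Much of this stands.

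- SAP 5.1.1 applies the testing procedure on the ITT-i set, so no confirmatory conclusion depends on this sentence.
- Missing 4 or more doses without ever missing three in a row requires repeated intermittent skipping. Protocol 7 works against that with re-dosing of recently missed doses, telephone checks on home-dosing days, and counts at visits.
- SAP 4.3 summarises compliance, and SAP 4.5 tabulates the reasons for per-protocol exclusion, so poor adherence would not be hidden.
- The general wording about major deviations might be used to exclude such a subject, although the SAP says that the listed criteria decide.

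Four stronger readings are tempting, and the documents do not support them.

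- *Neither limit does anything.* The rule still excludes every subject who exceeds both limits. Among early stoppers, whose misses are consecutive, 'or' and 'and' give the same result except for a subject who stops after dose 7.
- *The per-protocol analysis is lost as a check on the ITT-i result.* It still applies all its other criteria. It is weakened.
- *The 344 extra patterns measure how many subjects are wrongly admitted.* They count patterns with equal weight. The documents give no adherence data.
- *Seven missed doses is the maximum without qualification.* That figure requires counting from a scheduled slot before the first intake. SAP 2.2.2.2 leaves room for this by allowing the first dose on the day after randomization, but the protocol's definition of Day 1 points to counting from first intake, which gives 6.

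Probable intent does not remove the defect. If both limits were meant, the text says something else. If either was meant, the SAP should say so and give a reason.

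**Conclusion.** Wrong as written. Followed literally, the criterion admits subjects who took half the regimen, or as few as 4 of 10 doses counted from first intake and 3 of 10 counted from the first scheduled slot. It also admits subjects who missed three doses in a row. The conclusion rests on 10 planned doses for every subject and on the ordinary meaning of 'or'. It holds under either counting origin, since only the extreme value changes.

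The effect is limited to the supportive per-protocol analysis of the primary endpoint. Its size in subjects, or in the treatment estimate, cannot be derived from the documents.

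**What to change.** In the first criterion of SAP 2.2.2.2, replace 'or' with 'and', so that a subject must meet both the limit of 3 missed doses in total and the limit of 2 consecutive missed doses. Keep the early-dose requirement as it is. Add one sentence stating whether missed doses are counted from the first scheduled slot or from the first actual intake.

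With this change the most doses a per-protocol subject can miss is 3 of 10, and a run of three is excluded under either counting origin. If the sponsor did mean the limits as alternatives, the SAP should say so and justify it.

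The cost is one word and one sentence. Some less adherent subjects may leave a supportive set. SAP Amendments 2 and 3 already revised the per-protocol criteria, and membership is decided before database lock, so the edit belongs before those decisions are made.

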2.2.2.3. Intent-To-Treat non-infected (ITT-ni) Set

All subjects from the RAND analysis set who receive at least 1 dose of study drug and who do not have a confirmed infection with influenza A.

2.2.3. Safety Analysis Set

2.2.3.1. Safety Set or All Subjects Treated (AST)

All safety endpoints will be evaluated on the Safety population, consisting of all subjects who received at least one dose of study drug and will be analyzed by treatment arm as treated.

2.2.4. Pharmacokinetics (PK) Analysis Set

The PK analysis set is defined as subjects who have received at least 1 dose of pimodivir and have at least 1 valid blood sample drawn for PK analysis.

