### **11.1. Analysis Sets**

The efficacy endpoints will be analyzed on the Intent-to-Treat-infected (ITT-i) set, consisting of all subjects who were randomized, treated and had a confirmed influenza A infection, and will be analyzed by treatment arm as randomized.

The primary endpoint will also be analyzed on the Per Protocol set, consisting of all subjects in the ITT-i set without major protocol deviations that have an effect on efficacy and who were not prematurely unblinded during the study.

All safety endpoints will be evaluated on the Safety population, consisting of all subjects who received at least one dose of study drug and will be analyzed by treatment arm as treated.

Pharmacokinetic data will be evaluated on subjects in the ITT-i set who received pimodivir. Subjects will be excluded from the population PK analysis if their data do not allow for accurate assessment of the PK parameters (eg, incomplete administration of the study drug; missing information of dosing and sampling times).

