2.2.5. Pharmacodynamics (PD) Analysis Set

The PD analysis set is defined as all subjects in the PK analysis set for whom at least one PK parameter could be derived.

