9. PHARMACOKINETICS/PHARMACODYNAMICS

Blood samples for PK assessments of pimodivir will be collected from all subjects at the Day 3 and Day 6 visits.

Descriptive statistics of pimodivir plasma concentration over time will be tabulated for the PK analysis set.

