9.2. Pharmacokinetic/Pharmacodynamic Relationships

Pharmacokinetic/Pharmacodynamic relationships will be analyzed for the PD analysis set.

The exposure parameters AUC_{12h} and C_{trough} will be categorized into quartiles for the Day 3 visit, only C_{trough} will be categorized into quartiles for the Day 6 visit. Relationships of these parameters with the primary and selected secondary efficacy endpoints will be explored as follows.

Kaplan-Meier estimates for the time to resolution of the 7 primary influenza-related symptoms will be produced per each quartile for each exposure parameter.

The number and percentage of subjects with treatment-emergent adjudicated influenza complications will be tabulated for each quartile for each exposure parameter.

The number and percentage of subjects admitted to hospital within 28 days after treatment initiation will be tabulated for each quartile for each exposure parameter.

Kaplan-Meier estimates for the time to return to daily activities and for the time to resolution of fever will be produced per each quartile for each exposure parameter.

Relationships of AUC_{12h} with safety will be explored as follows. The number and percentage of subjects with the following treatment-emergent adverse events by AUC_{12h} quartile will be tabulated:

- Any AE
- AEs of worst grade 3 or 4
- Deaths due to AE
- Serious AEs
- AEs for which study drug was permanently stopped
- AEs at least possibly related to study drug
- Confirmed diarrhea events

A cross-tabulation of the worst treatment-emergent toxicity grades versus AUC_{12h} quartile will be presented for the laboratory parameters AST, ALT, and total bilirubin.

Separate tables will be produced for the worst treatment-emergent toxicity grades at Day 3 and overall.

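### The SAP's exposure-efficacy tables use a PD set with no infection condition, whereas protocol 11.1 puts PK data and efficacy endpoints on ITT-i, so subjects without centrally confirmed influenza A are pooled in

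*SAP*

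**What the plan says.** Protocol 11.1 sets two relevant rules. Efficacy endpoints are analyzed on ITT-i, and for PK: "Pharmacokinetic data will be evaluated on subjects in the ITT-i set who received pimodivir".

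The SAP keeps the first rule in section 2.2.2: "Efficacy will be analyzed on the intent-to-treat infected (ITT-i) set and by randomized treatment". It does not carry over the second. Section 2.2.4 defines the PK set as "subjects who have received at least 1 dose of pimodivir and have at least 1 valid blood sample drawn for PK analysis", and section 2.2.5 defines the PD set as "all subjects in the PK analysis set for whom at least one PK parameter could be derived". Neither mentions ITT-i or confirmed infection. Nor does sampling filter on infection. SAP section 9 states: "Blood samples for PK assessments of pimodivir will be collected from all subjects at the Day 3 and Day 6 visits".

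SAP 9.2 then names the population for the exposure analyses: "Pharmacokinetic/Pharmacodynamic relationships will be analyzed for the PD analysis set". For the primary endpoint it specifies: "Kaplan-Meier estimates for the time to resolution of the 7 primary influenza-related symptoms will be produced per each quartile for each exposure parameter". It asks for matching quartile outputs for adjudicated complications, hospital admission, time to return to daily activities and time to resolution of fever. The same section also contains exposure-safety tables.

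The SAP's Amendment 1 history records that analysis sets were added for PK and pharmacodynamic work. It gives no reason for a population different from the protocol's.

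**The concern.** Pimodivir inhibits the influenza A polymerase. A subject whose symptoms come from something else cannot show an antiviral exposure effect on those symptoms. Pooling such subjects with infected ones therefore pulls the exposure quartiles toward each other and tends to understate any exposure-response relationship for efficacy. Exploring that relationship is a stated secondary objective (protocol 2.1.1, SAP 1.1).

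The pooling is also out of line with the rest of the SAP. The efficacy sets in section 2.2.2 are either confirmed only (ITT-i, Per Protocol) or unconfirmed only (ITT-ni), and none mixes the two. ITT-ni is used only for the primary and the two most important secondary endpoints. Section 9.2 mixes both groups, and does so for return to daily activities and fever as well. A programmer following 9.2 literally would include every pimodivir subject with a derivable parameter.

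**Working it through.** **Step 1: the definitions side by side**

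| Source | Pimodivir dose | PK data condition | Infection condition |
|---|---|---|---|
| Protocol 11.1, PK data | yes | data adequate for the population PK analysis | ITT-i |
| SAP 2.2.4, PK set | at least one | at least one valid sample | none |
| SAP 2.2.5, PD set | inherited | at least one derived parameter | none |
| SAP 9.2, exposure-efficacy outputs | inherited | PD set | none |

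The general ITT-i rule in SAP 2.2.2 does not repair this, because 9.2 names its own set and does not intersect it with ITT-i.

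**Step 2: the plan's own use of the 15%**

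Inputs from SAP 1.4: 600 evaluable subjects, about 15% of those enrolled not centrally confirmed, 720 enrolled in total.

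- 600 / (1 − 0.15) = 706, within 2% of 720 ((720 − 706) / 720 = 1.9%).
- Conversely, 720 × 0.85 = 612, which covers the 600 needed.

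The 720 is therefore consistent with the 15%, and the same 15% can size this point.

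**Step 3: how many subjects are affected**

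Pimodivir arm: 720 / 2 = 360 as planned. At the maximum of about 1,080 (SAP 3.1), 1,080 / 2 = 540. The 15% is the documents' figure; 10% and 20% are assumed to show a range. The split between arms and across quartiles is assumed even.

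| Unconfirmed share | Of 360 (per quartile of 90) | Of 540 (per quartile of 135) |
|---|---|---|
| 10% | 36 (9) | 54 (13.5) |
| 15% | 54 (13.5) | 81 (about 20) |
| 20% | 72 (18) | 108 (27) |

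For each share these counts are upper limits, because a subject also needs a valid sample and a derived parameter.

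**Step 4: possible dilution, as an illustration**

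Assumptions, not figures for this relationship from the documents: log-logistic recovery times with scale 0.55 (the value in SAP 1.4), a true highest-to-lowest quartile median ratio of 0.75 in confirmed subjects, and the same time distribution but no exposure effect in a fraction d who are unconfirmed. With L(z) = 1 / (1 + exp(−z)), the observed median ratio y solves

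(1 − d) × L[(ln y − ln 0.75) / 0.55] + d × L[ln y / 0.55] = 0.5.

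The intercept cancels. Check for d = 0.15 at y = 0.783:

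- (−0.2446 + 0.2877) / 0.55 = 0.078, so L = 0.520.
- −0.2446 / 0.55 = −0.445, so L = 0.391.
- 0.85 × 0.520 + 0.15 × 0.391 = 0.50.

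The solutions are about 0.77 at d = 0.10, 0.78 at d = 0.15 and 0.79 at d = 0.20. At 15%, a 25% shorter median reads as about 22% shorter.

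**The case against.** The strongest case against is that this is an ambiguity with little consequence.

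- **The subjects concerned are not known to be uninfected.** A reader might infer that 9.2 pools in people without influenza A. The documents do not support that. Inclusion criterion 3 requires a positive local influenza A test. ITT-i requires central PCR confirmation, and SAP 2.2.2.1 also excludes anyone with no virology data. Subjects outside ITT-i lack central confirmation; some may be infected or of unknown status. This objection stands, and it means the dilution could be smaller than in step 4.
- **The protocol does not set a population for PK/PD.** A reader might infer that the protocol requires ITT-i for the exposure-response analysis itself. It does not say so. The ITT-i sentence in 11.1 concerns PK data, and protocol 11.8 on PK/PD names no set. Protocol 11.7 lists data for everyone with available concentrations and allows pooling with other studies. This stands as a limit on wording. However, 11.1 places both the PK data and the efficacy endpoints on ITT-i, so the SAP definition still departs from it.
- **Other text may already cover it.** The SAP is to be read with the protocol, and its estimand concerns confirmed infection. This makes a deliberate choice to study unconfirmed subjects unlikely, but it does not override the explicit set named in 9.2.
- **The outputs carry little weight.** They are quartile Kaplan-Meier estimates and counts with no test or decision rule, and exposure quartiles are not randomized groups. The protocol sends the PK/PD results to a separate report, whose population is not visible here. This stands and keeps the point minor.
- **A dosed-and-sampled set suits safety.** It matches the all-treated Safety Set. This stands, so the change should be confined to the efficacy outputs and the PK set reconciliation.

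**Conclusion.** The conflict is real but small. As written, SAP 9.2 runs exposure-efficacy outputs on a set with no infection condition, while protocol 11.1 puts PK data and efficacy endpoints on ITT-i and the SAP gives no reason for the difference.

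If the sponsor's 15% holds, up to 54 of 360 pimodivir subjects, or up to 81 of 540, would be affected. The shift of an assumed ratio from 0.75 to about 0.78 further requires that none of them shows an exposure effect and that they spread evenly across quartiles. It is an illustration, not a forecast.

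A reader might infer that the primary result or type I error control is at risk. They are not: the primary analysis is on ITT-i, and the exposure tables lie outside the testing hierarchy in SAP 5.1.1. What is affected is how clearly a descriptive secondary objective can be read.

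**What to change.** In SAP 9.2, state that the exposure-efficacy outputs use PD-set subjects who are also in ITT-i, consistent with protocol 11.1 and SAP 2.2.2. Keep the full PD set for the exposure-safety tables. Reconcile the PK set in SAP 2.2.4 with protocol 11.1, either by restoring the ITT-i condition for PK evaluation or by stating and justifying the departure. If the condition is restored in 2.2.4, define the PD set so that the safety tables do not inherit it.

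The cost is a few lines of SAP text and no new data. The efficacy exposure tables would lose up to about 15% of their subjects: at the planned size, 360 − 54 = 306 would remain if every pimodivir subject were otherwise evaluable; at the maximum size, 540 − 81 = 459.
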